# 7.1.1.2. Treatment Duration and Compliance

### (1) Treatment Duration

Treatment Duration (days) = the latest date of (last visit in Double-blind Treatment Period or discontinuation in Double-blind Treatment Period) – first dose date + 1

### (2) Treatment Compliance

The subjects are supposed to take a dose every four weeks and totally 4 doses per protocol. Treatment compliance (%) =number of doses/ROUNDUP(treatment duration/28).

[figure not shown]

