10.18.2 Vital signs

Sitting blood pressure (systolic and diastolic) will be measured at all study visits, including Screening where vital signs are to be assessed. Sitting blood pressure will be measured using an automatic blood pressure recording device with an appropriate cuff size, after the subject has rested for at least 5 minutes in a sitting position. The same arm will be used for all measurements where possible. The Investigator will perform an overall evaluation of vital sign findings outside of the normal range for safety purposes; such results will be reported as either 'abnormal clinically significant (CS)', or 'abnormal not CS (NCS)'. Pulse rate and tympanic body temperature will also be measured. Abnormalities of clinical significance will be reported as AEs. Repeat measurements will be performed, if needed. In addition, at Visit 2, 5, 6 and 7, vital signs will also be measured at 15±5 minutes, 30±5 minutes and 60±10 minutes post study drug infusion.

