### 3. STUDY DESIGN

# 3.1. Study Design

This is a Phase 2, randomized, double-blind, placebo-controlled study, stratified by moderate or severe pain to evaluate safety and efficacy of MT-2990 in women with endometriosis-associated moderate to severe pain.

Following the Screening period, eligible subjects who have met all the eligibility criteria and have moderate or severe nonmenstrual pelvic pain, and dysmenorrhea will be randomized into the study. Approximately 38 subjects per arm will be enrolled. Subjects will be randomly allocated to 1 of 2 treatment groups (placebo or MT-2990) in a ratio of 1:1. A single

dose of placebo or

End-of-treatment (EOT) will occur at Week 12 (Visit 7) and primary and secondary efficacy endpoints will be assessed at the Week 16 (Visit 9) visit. Subjects who discontinue from the study will complete the procedures for Visit 9 within 10 days of discontinuation (or as soon as possible after the site becomes aware of the discontinuation).

During the Extended Follow-up period, visits will be conducted via a telephone call at Week 27 (Visit 10) and at Week 38 (Visit 11). Visit 11 will be the end of study (EOS) visit.

The Sponsor will be unblinded after Week 16 (Visit 9), while the Sites and subjects will remain blinded until the end of the Extended Follow-up period at Week 38 (Visit 11). During the study, database will be locked twice; Week 16 (Visit 9) to assess safety and efficacy, and at Week 38 (Visit 11) to assess other outcomes during the Extended Follow-up period.

The study design schema is presented in.

[figure not shown]
[figure not shown]
[figure not shown]
[figure not shown]

Figure 1 Study design schema

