# (2) Other endpoints

The analysis visits will be defined as following.

Analysis visit	Nominal day	Window
Baseline	Day 1	NA
Week 1	Day 8	Day 2 to 11
Week 2	Day 15	Day 12 to 20
Week 4	Day 29	Day 21 to 43
Week 8	Day 57	Day 44 to 71
Week 12 (EOT)	Day 85	Day 72 to 88
Week 13	Day 92	Day 89 to 99
Week 16	Day 113	Day 100 or after
Week 27	Day 190	NA
Week 38 (EOS)	Day 267	NA

EOT assessment data will be included as visit data in the applicable window.

The date of the first dose of study drug is defined as Day 1. If the data at Day 1 is missing, the last data before Day 1 will be used for baseline. If one visit corresponds to both window of

week 12 and 13, the visit will be applied an analysis visit which matches visit on case report form (CRF). For other visits, if there are multiple data in a window, the closest data to nominal day will be used. If more than one data in the window with the same distance to the nominal day, the data of later date will be used. For Week 27 and 38, CRF visit will be used as analysis visits.

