# 8.1.5. Treatment Duration and Compliance

Treatment duration and compliance will be summarized on the SAF and ITT population. Treatment duration and compliance will be listed on the RAND population.

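### The SAP's compliance formula expects a fifth dose from Day 113, so a fully dosed completer seen on the nominal Week 16 day is reported as 80% compliant

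*SAP*

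**What the plan says.** SAP 7.1.1.2 (2) sets the target first: "The subjects are supposed to take a dose every four weeks and totally 4 doses per protocol". It then gives the formula "Treatment compliance (%) =number of doses/ROUNDUP(treatment duration/28", closing the bracket with no cap and no further condition in the readable text.

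SAP 7.1.1.2 (1) defines treatment duration as an end date minus the first dose date, plus 1. The end date is "the latest date of (last visit in Double-blind Treatment Period or discontinuation in Double-blind Treatment Period", that is, the later of the two.

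Other sections fix the timing:

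- SAP 3.1 places end of treatment at Week 12 (Visit 7). Protocol section 12 ends the double-blind period at Visit 9, which is Week 16.
- Protocol 10.18.2 requires post-infusion measurements "at Visit 2, 5, 6 and 7, vital signs will also be measured at" set times, which identifies four infusion visits.
- SAP 7.3 (2) numbers the first dose date as Day 1, gives Week 16 a nominal day of 113, and sets its analysis window as "Day 100 or after".

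On reporting, SAP 8.1.5 states: "Treatment duration and compliance will be summarized on the SAF and ITT population". It also lists both variables on the randomized population.

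**The concern.** The numerator can only reach 4. The denominator counts 28-day blocks, started or completed, up to the last double-blind visit, and that visit comes four weeks after the last planned dose. The nominal days 29, 57, 85 and 113 each lie one day past a multiple of 28, so rounding up adds one expected dose on each of them. That is correct for Days 29, 57 and 85, which are dosing days. It is wrong for Day 113, when no dose is planned.

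Reported compliance would then depend on the date of the Week 16 visit as well as on doses received. A table reading about 80% would suggest missed infusions that did not occur. Any difference between arms in visit timing or drop-out would enter the compliance comparison; its size and direction cannot be worked out from the documents.

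**Working it through.** **Inputs.** Four planned doses at 28-day intervals (SAP 7.1.1.2), hence nominal dosing Days 1, 29, 57 and 85. Day 1 is the first dose date and Week 16 is nominally Day 113 (SAP 7.3). The last double-blind visit is Visit 9 (Protocol section 12).

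**Duration.** For a last visit on study day d, duration = d − 1 + 1 = d days.

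**Formula.** Denominator = d/28 rounded up to a whole number. Compliance = 100 × doses / denominator. Two readings are assumed: ROUNDUP without a digits argument means rounding up to an integer, and the percent sign implies the factor of 100 that the formula does not show.

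**Where the planned figure of 4 is reproduced.** 85/28 = 3.036, which rounds up to 4; 100/28 = 3.571 gives 4; 112/28 = 4.000 gives 4. For Days 85 to 112 the denominator equals the four planned doses.

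**Where it fails.** 113/28 = 4.036 gives 5; 140/28 = 5.000 gives 5; 141/28 = 5.036 gives 6; 168/28 = 6.000 gives 6.

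| Last double-blind visit | Denominator | All 4 doses | 3 doses |
|---|---|---|---|
| Days 100–112 | 4 | 100% | 75% |
| Days 113–140 | 5 | 80% | 60% |
| Days 141–168 | 6 | 66.7% | 50% |

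The third row shows what the formula returns for very late visits. It does not claim that such visits are likely. It does show that the ordering can reverse: a subject who missed one dose and was last seen by Day 112 (75%) ranks above a fully dosed subject last seen on Day 141 (66.7%).

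**Effect on a group mean.** The share of completers seen on Day 113 or later is not given. As an assumption, let a share p of fully dosed completers be seen on Days 113–140 and the rest on Days 100–112. Their mean is 80p + 100(1 − p) = 100 − 20p percent: 100% at p = 0, 90% at p = 0.5 and 80% at p = 1. The true value is 100% throughout.

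**Would dropping the plus 1 repair it?** No. Day 113 would give 112/28 = 4, but Day 114 would give 113/28 = 4.036 and so 5. Day 85 would give 84/28 = 3, so four doses would read 4/3 = 133.3%.

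**Does a cap repair it?** MIN(4, ROUNDUP(d/28)) equals 4 for every d from 85 upward, so a fully dosed completer reads 100% on any visit date.

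**Early termination.** SAP 3.1 says: "Subjects who discontinue from the study will complete the procedures for Visit 9 within 10 days of discontinuation". Take doses on Days 1 and 29, discontinuation on Day 50 and the termination visit on Day 60. If that visit counts as the last double-blind visit, 60/28 = 2.143 rounds up to 3 and compliance reads 2/3 = 66.7%. At discontinuation, 50/28 = 1.786 rounds up to 2, giving 2/2 = 100%. The cap does not affect this case.

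**The case against.** The strongest counter-argument concerns importance. Compliance feeds no visible test, population or decision rule; the per-protocol definition in SAP section 5 names no compliance threshold. Infusions are given on site under supervision, with dosing times and departures recorded (Protocol 11.3), so the true dose count is known and an 80% figure in a four-infusion trial might be recognised as an artefact. That correctly limits the consequence, but the SAP would still produce a wrong number in a planned table, on its own nominal visit day.

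Second, a figure that is not reproduced follows the formula and could contain a cap. This stands as a caveat. If a cap exists there, the sponsor can confirm it at once.

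Third, the open-ended Week 16 window assigns data to analysis visits; it does not authorise a Visit 9 as late as Day 141, and the operational visit window is not readable. That is fair. The 66.7% figure is therefore only a formula output, while the 80% figure needs nothing beyond the nominal day.

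Fourth, whether a dose falling between discontinuation and a termination visit should count as expected is partly a choice of definition. This also stands: the early-termination example is conditional and secondary to the completer error.

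Finally, neither a cap nor a count of nominal days handles early dosing. Doses on Days 1 and 27 with a stop on Day 28 give 2/1 = 200% under both. The definition of expected doses has to allow for this.

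**Conclusion.** The concern holds. As written, the formula gives a denominator of 5 on the nominal Week 16 day against four planned doses, so a fully dosed completer last seen on Days 113 to 140 is reported as 80%, against 100% one day earlier. The arithmetic is certain for the readable formula, given the two readings of ROUNDUP and the percent sign stated above. It remains possible that the unreproduced figure contains a cap. How many completers are affected depends on actual visit dates, which the documents do not give.

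The consequence is limited to descriptive compliance output on the safety, ITT and randomized populations. It should be corrected, but it does not bear on the efficacy conclusions.

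**What to change.** Before the Week 16 database lock, replace the denominator with an explicit count of expected doses, and write the factor of 100 into the formula.

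- **Preferred:** count the scheduled dosing visits (Day 1, Weeks 4, 8 and 12) that the subject attended, or whose nominal day fell on or before the date of discontinuation. For completers this is always 4. It gives 2 of 2 in both the early-termination and the early-dosing examples. The SAP should name the date that ends participation for this purpose and say that the termination visit does not extend it.
- **Minimum:** MIN(4, ROUNDUP(treatment duration/28)). This corrects every completer but leaves the early-termination and early-dosing cases as they are.

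The minimum costs one line of SAP text and one line of code. The preferred version needs a sentence or two more. Neither needs new data, and neither alters dosing or the visit schedule.

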# 7.1.2. Efficacy assessments

#### 7.1.2.1. Baseline Definitions

[figure not shown]
The baseline value for assessments using e-Diary will be based on the average of the last 35 calendar days during the screening period. For assessments that are measured for the first time on Study Day 1, use the Study Day 1 results for the baseline value. The Baseline value for other variables is defined as the last non-missing value prior to first dose of the study drug unless otherwise specified.

[figure not shown]
All baseline efficacy data will not be imputed, unless otherwise specified.

# 7.1.2.2. Pain assessment of nonmenstrual pelvic pain, dysmenorrhea and dyspareunia

[figure not shown]
be calculated.

[figure not shown]

[figure not shown]
# 7.1.2.5. Other assessment using e-Diary data

[figure not shown]
• Pill count of any rescue analgesic used

Number of days with opioid use

# 7.1.3. Safety Assessments

### 7.1.3.1. Adverse Events

Adverse events will be coded according to the MedDRA version 21.1

[figure not shown]
- (1) Treatment Emergent Adverse Events (TEAEs)
  - AEs are considered as treatment emergent if they newly occur after the first dose administration of study medication or if a predose event increases in severity following dosing.
- (2) Adverse Events of Special Interest (AESI) All fractures.

[figure not shown]
# 7.1.3.2. 12-Lead ECGs

- (1) Criteria for pre-defined limit
  - post-baseline QTcF > 450 msec
  - Baseline QTcF < 450msec and post-baseline QTcF > 450msec, 480msec, 500msec
  - Change from baseline QTcF > 30msec, 60msec

# 7.1.4. Pharmacokinetics Evaluation

# (3) Safety endpoints

• Adverse events (AE):

If severity/relationship is found to be missing, the most severe/reasonable possibility will be imputed respectively for the summary of interest.

For AE start and/or end date missing or partial dates, the AE will be treated as TEAE if it cannot be determined as a non-TEAE.

• Other safety data:

For safety summaries, only observed data will be used. Unless otherwise specified. Missing safety data will not be imputed.

# 7.3. Analysis Visit Definitions

(1) Efficacy endpoints derived from e-diary data

Analysis visit window for assessments using e-Diary will be based on the study day of the specific visit. The analysis visits and windows are defined as the following.

Analysis visit	Study Day of Monthly PGIC Assessments	Window $(W_x)$
Baseline	NA	Last 35 days prior to Day 1
Week 4	X 1	$max(1, X_1 - 35) < W_4 \le X_1$
Week 8	X 2	$max(X_1, X_2 - 35) < W_8 \le X_2$
Week 12	X 3	$max(X_2, X_3 - 35) < W_{12} \le X_3$
Week 16	X 4	$max(X_3, X_4 - 35) < W_{16} \le X_4$

The date of the first dose of study drug is defined as Day 1. If monthly assessment is missing, following rules will be applied to impute a study day.

- If the date of assessment at Week 4 is missing, the date of vital sign assessment will be set as the study day. If the date of vital sign assessment is missing, the study day is set to be 28.
- If the date of assessment at Week 8, 12, or 16 is missing, the date of vital sign assessment will be set as the study day. If the date of vital sign assessment at Week 8, 12, or 16 is missing, the study day is set to be the preceding month's day + 28.

The window for assessment is defined in following section.

# (2) Other endpoints

The analysis visits will be defined as following.

Analysis visit	Nominal day	Window
Baseline	Day 1	NA
Week 1	Day 8	Day 2 to 11
Week 2	Day 15	Day 12 to 20
Week 4	Day 29	Day 21 to 43
Week 8	Day 57	Day 44 to 71
Week 12 (EOT)	Day 85	Day 72 to 88
Week 13	Day 92	Day 89 to 99
Week 16	Day 113	Day 100 or after
Week 27	Day 190	NA
Week 38 (EOS)	Day 267	NA

EOT assessment data will be included as visit data in the applicable window.

The date of the first dose of study drug is defined as Day 1. If the data at Day 1 is missing, the last data before Day 1 will be used for baseline. If one visit corresponds to both window of

week 12 and 13, the visit will be applied an analysis visit which matches visit on case report form (CRF). For other visits, if there are multiple data in a window, the closest data to nominal day will be used. If more than one data in the window with the same distance to the nominal day, the data of later date will be used. For Week 27 and 38, CRF visit will be used as analysis visits.

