9.1.5 Early Termination

For all subjects, Visit 9 ([ET], Week 16) assessments should be performed, per the Schedule of Assessments (Table 2).

Any unresolved AE or SAE will be followed up according to Section 12.

In the event that a subject elects not to return to the clinical site for the ET Visit, the Investigator must make every effort to contact the subject to review all AEs. In the event that a subject drops out of the study at any time, the reason for discontinuation must be fully documented in the source documents and the eCRF. The Investigator site personnel will document the AEs and any other assessments in the source documents and will make every effort to complete all required EOS assessments.

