#### 6. STATISTICAL CONSIDERATIONS

### 6.1. Descriptive Statistics

### (1) Non-PK related

Continuous data will be summarized descriptively using the number in the analysis set (N), the number of observations (n), mean, standard deviation (SD), median, minimum and maximum. Categorical data will be summarized using frequency counts and percentages. The denominator for the percentages will be the total number of subjects in the treatment group or analysis population being presented, unless otherwise specified.

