### 8.3.4. 12-Lead ECGs

Absolute values and changes from baseline will be summarized for the following parameters.

- Heart Rate (bpm)
- PR (msec)
- QRS (msec)
- QT (msec)
- QTcF (msec)
- QTcB (msec)

The percentage of subjects with 12-lead ECG values outside pre-defined limit will be summarized.

All data will be listed.

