# (2) Safety

Analysis Visit	Apply to		
	Laboratory Tests	Vital Signs	12-Lead ECGs
Baseline	X	X	X
Week 1	X	X	
Week 2	X	X	·
Week 4	X	X	
Week 8	X	X	
Week 12 (EOT)	X	X	
Week 13	X	X	
Week 16	X	X	X
Week 27			
Week 38 (EOS)			

Unscheduled visits will not be displayed in by-visit summary tables but will be included in the data listings.

In by-visit summary tables for interim safety assessment, limited analysis visits will be reported. The first interim safety assessment will report baseline to Week 2. The second interim safety assessment will report baseline to Week 4. The third interim safety assessment will report baseline to Week 16. All visit will be included in the data listing.

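### An early-termination ECG dated before Day 100 has no row in the by-visit ECG summary, and the SAP does not say whether the QTcF limit summary picks it up

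*SAP*

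**What the plan says.** **Early leavers.** Protocol 9.1.5 states: "For all subjects, Visit 9 ([ET], Week 16) assessments should be performed, per the Schedule of Assessments (Table 2". SAP 3.1 gives the timing: "Subjects who discontinue from the study will complete the procedures for Visit 9 within 10 days of discontinuation", or as soon as possible once the site knows. An ET visit is thus Visit 9 carried out early.

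**Assignment to visits.** SAP 7.3(2) places non-diary data in windows by study day, and Week 16 is "Day 100 or after". The CRF visit decides only when a visit fits both Week 12 and Week 13, and for Weeks 27 and 38. Early Visit 9 data have no such override. The sentence "EOT assessment data will be included as visit data in the applicable window" does not supply one, because SAP 3.1 says "End-of-treatment (EOT) will occur at Week 12 (Visit 7".

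**Visits reported.** The grid in SAP 9.3(2) marks ECGs at Baseline and Week 16 only. Laboratory tests and vital signs are marked at every visit from Baseline to Week 16. The same section adds: "Unscheduled visits will not be displayed in by-visit summary tables but will be included in the data listings".

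**QTcF limits.** SAP 8.3.4 states: "The percentage of subjects with 12-lead ECG values outside pre-defined limit will be summarized". The criteria in SAP 7.1.3.2 refer to post-baseline QTcF and name no visit. SAP 6.1 sets the default denominator: "The denominator for the percentages will be the total number of subjects in the treatment group or analysis population being presented", with room for exceptions stated elsewhere.

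**The concern.** The plan collects an ECG from women who leave early, yet its own windows send most such ECGs to visits where no ECG is tabulated. Laboratory tests and vital signs do not have this problem, since every window up to Week 16 has a row for them.

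The ECGs left out are unlikely to be a random subset. Protocol 8.5 lists safety reasons for withdrawal, among them hypersensitivity reactions and haematological and liver limits. The by-visit ECG summary would then mainly describe women who stayed to about Day 100. Safety and tolerability is a secondary objective, and the ECG listing keeps the values without comparing the arms.

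**Working it through.** **1. The plan's own figure.** Inputs from SAP 3.3: difference 0.5, SD 0.65, two-sided 5% two-sample t-test, 25% drop-out. With the noncentral t distribution, 28 per arm gives power 0.807 and 27 gives 0.792, so 28 per arm is reproduced. Allowing for drop-out: 28 / (1 − 0.25) = 37.3, rounded up to 38 per arm, and 2 × 38 = 76. These figures are not disputed. They serve only to size this point.

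**2. Where an ECG falls.** Windows from SAP 7.3(2), ECG rows from SAP 9.3(2):

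| Day of ECG | Analysis visit | ECG row? |
|---|---|---|
| 2–11 | Week 1 | No |
| 12–20 | Week 2 | No |
| 21–43 | Week 4 | No |
| 44–71 | Week 8 | No |
| 72–88 | Week 12 | No |
| 89–99 | Week 13 | No |
| 100 or later | Week 16 | Yes |

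The windows have no gaps. From Day 2 to Day 112, the day before nominal Week 16 (Day 113), there are 111 possible ECG days. Of these, 98 (Days 2–99) have no ECG row and 13 (Days 100–112) count as Week 16.

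**3. The cut-off is the ECG date, not the leaving date.** If a woman leaves on Day L and the 10-day limit is met, her ECG falls between Day L and Day L + 10.
- L ≤ 89: the latest ECG day is 89 + 10 = 99, so the ECG has no row.
- L = 90 to 99: the ECG can fall on Day 100 or later and then counts as Week 16.
- If the ET visit comes later than 10 days, as the plan allows, some women with L below 90 could also reach Day 100.

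**4. How many women.** 0.25 × 76 = 19 in total and 0.25 × 38 = 9.5 per arm. The number affected equals this only if every drop-out has an ET ECG dated before Day 100. Protocol 8.5 foresees women who do not return for that visit, and step 3 shows that others reach the Week 16 window. The documents give no drop-out timing, so the figure cannot be narrowed.

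**5. The QTcF limit summary.** It is a percentage of subjects, its criteria name no visit, and the bar on unscheduled data covers by-visit tables only. As worded, it can include ET and unscheduled ECGs, but nothing says that it must. Under the default denominator, a woman with no post-baseline ECG adds one to the denominator and nothing to the numerator, just like a woman whose ECG was within limits.

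**The case against.** The strongest reply is that nothing is lost and the choice is declared. All ECG data are listed. Protocol 10.18.3 requires clinically significant ECG abnormalities to be reported as adverse events, and SAP 8.3.1 tabulates TEAEs, including those leading to discontinuation. The trial is a 76-woman proof-of-concept study with descriptive ECG summaries. Part of the text is also unavailable: the Schedule of Assessments (Protocol Table 2) is absent, and most of SAP 7.2 on missing data is not visible, so an ET rule could stand there.

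Much of this stands. It limits the point to the by-visit ECG summary, and it means that a clinically significant abnormality in an early leaver should still reach a table. It does not remove the point: adverse event tables depend on the investigator's judgement of significance and do not show change in QTcF, PR or heart rate by arm.

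A reader might infer more than the documents support:
- **That the SAP has a stated rule for ET data.** The sentence on EOT concerns Week 12. The result follows from the day windows and the reporting grid together.
- **That the QTcF percentages omit early leavers.** The summary is not tied to a visit, so this is an ambiguity, not a stated exclusion.
- **That laboratory results are lost in the same way.** ET laboratory values have a row in every window to Week 16. Unscheduled values are openly kept to listings, and SAP 6.1 reports the minimum and maximum, so an extreme tabulated value is visible. A worst-value laboratory table would be a preference.
- **That the bias has a known direction.** The documents give no withdrawal rates by arm or by reason.

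**Conclusion.** The point holds for ECGs. Followed as written, SAP 7.3(2) and 9.3(2) leave an ET ECG dated Day 2–99 out of the by-visit summary by arm, although it is collected and listed. At most about 9 to 10 of 38 women per arm (19 of 76) are affected at the planned drop-out, and probably fewer. For the QTcF limit summary the fault is narrower: the SAP does not state which ECGs count, and the default denominator treats a woman without a post-baseline ECG as free of exceedance.

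This rests on three assumptions: that Visit 9 includes an ECG and no earlier post-baseline visit does, which is inferred from the reporting grid; that the 25% planning figure is realistic; and that no ET mapping rule stands in the text that is not available. It is a cheap improvement to a secondary safety summary and does not touch the efficacy analysis.

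**What to change.** Keep the windowed Week 16 row and make two changes.

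1. **SAP 8.3.4 and 9.3(2):** add an ECG row labelled Week 16/ET (last post-baseline), so that an ECG from a Visit 9 done early is tabulated by arm whatever its study day.
2. **SAP 8.3.4:** state that the QTcF limit percentages use any post-baseline ECG, whether scheduled, ET or unscheduled, and that the denominator is the women with at least one such ECG.

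The cost is a few lines of SAP text and one extra table row, from data already collected. The drawback is that the Week 16/ET row mixes different times since the last dose, so it needs a footnote saying so.

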12 ADVERSE EVENT MANAGEMENT

All AEs and SAEs will be recorded in the source documents. All SAEs that occur from the time written ICF is obtained until the end of the Double-blind Treatment Period (Visit 9), and all AEs that occur from Day 1 until the end of the Double-blind Treatment Period (Visit 9) will be recorded in the eCRF. Even if the AE is assessed by the Investigator as not related to study medication, its occurrence must be recorded in the source documents and eCRF. AEs will be classified as 'treatment-emergent' if they arise following the administration of study medication or if a predose illness increases in severity following dosing.

At each study visit, after the subject has had an opportunity to spontaneously mention any problems, the Investigator should inquire about the occurrence of AEs. The questioning should be open-ended and nonleading.

Post each study drug infusion, subject should be observed for approximately 60 ± 10 minutes. During this period, vital signs must be obtained at 15 ± 5 minutes, 30 ± 5 minutes and 60 ± 10 minutes. A patient instructions sheet will be provided to all subjects with instructions to observe and report all possible adverse events such as infusion related or infections in particular.

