14.3.4.4 Safety Evaluation

AEs are considered as treatment emergent if, they occur after the first dose administration of study medication or if a predose event increases in severity following dosing. The frequency and incidence of TEAEs will be summarized by system organ class (SOC) and preferred term (PT), by treatment arm and overall. Summary listings will be constructed by relationship to study medication and by maximum severity. Serious TEAEs and TEAEs leading to study medication discontinuation will be provided as listings. All fractures will be collected as AESI.

Vital signs, ECG parameters, and clinical laboratory results will be summarized by treatment arm and planned sampling point.

Other safety measures (eg, bone fractures, DEXA scan) will be summarized according to the data type.

Physical examination data will be listed by subject. Changes in physical examinations will be described in the text of the CSR.

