# 8.3.3. Vital Signs

Absolute values and changes from baseline will be summarized for the following parameters.

- Systolic Blood Pressure (mmHg)
- Diastolic Blood Pressure (mmHg)
- Pulse Rate (bpm)
- Body Temperature (°C)

All data will be listed.

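### Does the SAP need to say which same-day vital-sign reading counts at the infusion visits, and add rows for the post-infusion readings?

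*SAP*

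**What the plan says.** Protocol 10.18.2 requires vital signs at the study visits where they are scheduled. It adds that at Visits 2, 5, 6 and 7 "vital signs will also be measured at 15±5 minutes, 30±5 minutes and 60±10 minutes post study drug infusion". Protocol Section 12 makes the timed readings mandatory after each infusion ("During this period, vital signs must be obtained at" those three times). On dosing, SAP 7.1.1.2(2) states: "The subjects are supposed to take a dose every four weeks and totally 4 doses per protocol".

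On analysis, Protocol 14.3.4.4 says: "Vital signs, ECG parameters, and clinical laboratory results will be summarized by treatment arm and planned sampling point". SAP 8.3.3 lists four parameters to be summarized as values and changes from baseline, names no time point within a visit, and ends with "All data will be listed". The safety grid in SAP 9.3 marks vital signs once per analysis visit. It also limits the interim by-visit tables; for example, "The first interim safety assessment will report baseline to Week 2".

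SAP 7.3(2) assigns data to windows by study day. Where several values share a window, the closest to the nominal day is taken. If that still ties, the SAP says: "If more than one data in the window with the same distance to the nominal day, the data of later date will be used". Baseline, under SAP 7.1.2.1, is "defined as the last non-missing value prior to first dose of the study drug". That sentence stands under the efficacy heading but covers other variables generally.

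**The concern.** Distance in days and calendar date cannot separate readings taken on the same date. At an infusion visit one scheduled reading and three timed readings share a date, so the Week 4, 8 or 12 value could be any of the four. If a programmer read the tie-break as date and time, the 60-minute post-infusion reading would win and be compared with a pre-dose baseline. Nothing suggests that this is intended.

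The Day 1 timed readings look stranded as well. They come after the first dose, so they are not baseline, and the Week 1 window opens on Day 2.

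What seems to be at stake is the comparison of arms on blood pressure, pulse and temperature shortly after infusion. The DMC's stated focus (Protocol 15.3, SAP 4.3) includes infusion site reactions, hypersensitivity and cytokine release syndrome. Yet the first interim by-visit table, taken literally, would contain no post-infusion reading.

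**Working it through.** The plan gives no figure of its own to reproduce here. The check applies the SAP rules literally, counts what is affected, and then asks whether the literal reading is the one the plan calls for.

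**Inputs**
- Timed readings: 3 per infusion visit, at Visits 2, 5, 6 and 7 (Protocol 10.18.2).
- Doses: 4, four-weekly (SAP 7.1.1.2).
- Visit 7 is Week 12 (SAP 3.1). Visits 5 and 6 as Weeks 4 and 8 are inferred from visit order and the dosing interval.
- Windows (SAP 7.3(2)): Week 4, nominal Day 29, Days 21 to 43; Week 8, Day 57, Days 44 to 71; Week 12, Day 85, Days 72 to 88; Week 1 opens on Day 2.

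**Literal application**
- Readings per infusion visit: 1 scheduled + 3 timed = 4, all on one date.
- Visit on its nominal day: all four are at distance 0 and share a date, so 4 enter and 4 remain.
- Visit 2 days late (Days 31, 59, 87) or 2 days early (Days 27, 55, 83): all four are at distance 2, and again 4 remain.
- Day 1: the 3 timed readings fall in no post-baseline window.

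**Counts per parameter, if every infusion is given**
- Per subject: 4 × 3 = 12, of which 3 are on Day 1 and 3 × 3 = 9 at Weeks 4, 8 and 12.
- All subjects: 12 × 76 = 912.
- First interim, 20 subjects: 20 × 3 = 60, none of them in a baseline-to-Week-2 window.
- Second interim, 50% of 76 = 38 subjects: 38 × 3 = 114 on Day 1 and 38 × 3 = 114 at Week 4, together 228.

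The planned 25% drop-out (Protocol 14.1) makes 912 an upper bound.

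**Is the literal reading the one the plan calls for?**
1. The SAP Introduction gives precedence to analysis details that the SAP describes. SAP 8.3.3 describes no rule for time points within a visit, so Protocol 14.3.4.4 is not displaced.
2. SAP Section 10, which lists changes from the protocol, removes one endpoint and adds two. It does not drop the commitment to summarize by scheduled time point.
3. SAP 7.3(2) defines analysis visits, and its overlap rules speak of visits. It can fairly be read as choosing between visits. Protocol 10.18.2 presents the 15, 30 and 60-minute readings as additional to the visit reading, so they are separate scheduled points.
4. Applied within scheduled time point, the window rule gives each point one candidate at an infusion visit (4 readings ÷ 4 points = 1), and the tie disappears. Day 1 timed readings are then summarized under their own time point and need no post-baseline visit window.
5. The 9.3 grid shows which visits are reported for each assessment. A list of visits is weak evidence that time points within a visit will not be tabulated.

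**What a poor choice could cost.** Any single choice made the same way in both arms still gives a like-for-like descriptive comparison; what changes is the time point it describes.

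**The case for a change.** The strongest case for a change is that the SAP solves this kind of problem elsewhere and not here. It uses the CRF visit label to settle Week 12/13 overlaps and for Weeks 27 and 38, and it summarizes serum concentrations by nominal sampling time. Vital signs get neither device, so a programmer working only from SAP 7.3, 8.3.3 and 9.3 could produce one row per visit. The safety setting adds weight: the only earlier clinical study gave single doses to healthy men (Protocol 7.2.1), whereas this trial gives repeated infusions to women with endometriosis. Adverse event tables capture only changes judged clinically significant, so a modest mean shift between arms would not appear there.

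The literal tie stands, and so does the point about modest mean shifts. Neither shows a wrong rule, because the protocol already calls for the summary that would reveal such a shift. The interim argument is weaker. Interim listings include all visits (SAP 9.3), the DMC receives adverse event lists monthly and may ask for more (Protocol 13.1), and its charter, not among the documents supplied, sets its scope. The SAP rests on an amendment dated 04 March 2020, after the estimated last-subject completion of February 2020, so some or all interims may already have been run.

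**Conclusion.** No change to the plan is needed. This is a gap in detail that analysts would fill sensibly: keep the scheduled visit reading as the by-visit value and tabulate the timed readings under their own time points, as Protocol 14.3.4.4 says. Spelling out the timed rows in the SAP would repeat a protocol commitment, and adding change from a same-day reference is an optional display in a 76-subject exploratory study.

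The effect is confined to descriptive vital-sign tables: at most 3 of the 7 post-baseline visit rows (Weeks 4, 8 and 12 among Weeks 1, 2, 4, 8, 12, 13 and 16), plus the display of the Day 1 timed readings. Listings, adverse event reporting, DMC access to data and all efficacy analyses are untouched. The counts of 912, 60 and 228 describe planned readings and say nothing about how far any mean would move.

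This rests on three assumptions: that Protocol 14.3.4.4 applies where the SAP is silent; that Visits 5 and 6 are Weeks 4 and 8; and that the time-point label is recorded with each reading. The Schedule of Assessments and the table shells are not in the text supplied, so whether the visit reading precedes the infusion could not be checked.
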